5.2 Variables Used for Stratification of Randomization

At Visit 2, subjects will be randomized in blocks to double-blind treatments, stratified by weight (≤ 100 kg vs. > 100 kg) and prior exposure to TNF antagonists (0 vs. ≥ 1). Subjects will be randomized to risankizumab or adalimumab in a ratio of 1:1 within each level of stratification.

Subjects patients initially on adalimumab and \geq PASI 50 and $<$ PASI 90 will be re-randomized at Week 16 in a 1:1 ratio to receive either risankizumab or adalimumab. Re-randomization will also be stratified by weight (≤ 100 kg vs. > 100 kg) and prior exposure to TNF antagonists (0 vs. ≥ 1).

6.0 Analysis Conventions

Definition of Baseline:

The last non-missing measure collected on or before the date of the first dose of study drug injection will be used as Baseline for summary of demographics and disease characteristics, efficacy analyses, and safety analyses in each period, with the exception that:

- The last evaluation on or prior to the first dose date of risankizumab will be used for the safety analyses for ALL_RZB populations.
- For all vital sign assessments, only assessments prior to first dose time will be considered, since vital signs are to be assessed both pre- and post-dose in some visits.

For subjects who are randomized but do not take any study drug during the study, the last non-missing measurement collected on or before the date of randomization will be used as Baseline.

Definition of Final Observation (Applicable to Safety Analyses):

Final observation for the Part A is defined as:

- The last non-missing observation collected within 105 days following the last dose of study drug in Part A for subjects who were not dosed in Part B.
- The last non-missing observation collected on or before the first dose date of study drug on or after Week 16 and within 105 days following the last dose of study drug in Part A for subjects who were dosed in Part B. For vital sign assessments, only assessments prior to the first dose of study drug injection in Part B will be included in the analysis for Part A.

Final observation in Part B and in the entire study is defined as the last non-missing observation collected within 105 days after the last dose of study drug.

Definition of Rx Days (Days Relative to the Date of First Dose of Study Drug)

Rx days are calculated for each time point relative to the date of first dose of study drug. They are defined as the number of days between the day of the first dose of study drug and the specific time point. Rx days are negative values when the time point of interest is prior to the first study drug dose day. Rx days are positive values when the time point of interest is on or after the first study drug dose day. The day of the first dose of study drug is defined as Rx Day 1, while the day prior to the first study drug dose is defined as Rx Day -1 (there is no Rx Day 0).

For analysis in each Part (A or B), the Rx Day is calculated relative to the first dose of study drug in the specific study Part. For analysis across Part A and Part B, the Rx days are calculated relative to the date of first dose of study drug injection in Part A.

Definition of Analysis Windows

All time points and corresponding time windows are defined based on Rx Days.

For efficacy analyses, local tolerability, laboratory parameters, and vital sign variables, analysis windows are constructed using the following algorithm:

- Determine the nominal Rx day for each visit (e.g., Week 4 [4 weeks after Baseline visit] equals Rx Day 29).
- In order to include all post baseline data, the first post-baseline interval starts on the first day after the first dose of study drug (Rx Day 2).
- Determine the window around a specific nominal Rx day by adding or subtracting half of the interval between adjacent visits (e.g., days between Week 2 and Week 4 is 14). The threshold between adjacent visits is determined by splitting the interval evenly between the visits. If the resulting split is between Rx days, then the threshold is determined as the midpoint between the adjacent visits. If the resulting split is on an Rx day, then the threshold is determined as being between that Rx day and the Rx day prior to it (e.g., the split between Week 2 and Week 4 would be between Rx Days 22 and 23).
- If more than one assessment is included in a time window the assessment closest to the nominal day will be used. If there are two observations equidistant to the nominal day, the one after the nominal day will be used in analyses. If more than one assessment is included on the same day, then the worst assessment on that day will be used in analyses, except those specified in Section 11.0.

The protocol specified visits and corresponding time windows used in the efficacy analyses, local tolerability, ECG, laboratory parameters, and vital sign variables, are presented in the following tables.

Table 4. Visit Windows for PASI/sPGA and Vital Signs for Part A (ITT_A/PP_A/Safety_A Populations)

Window Label	Target Day	Time Window
Baseline	1	$\leq 1^a$
Week 4	29	[2, 43]
Week 8	57	[44, 71]
Week 12	85	[72, 99]
Week 16	113	[100, 127 ^b]

Rx Day calculated relative to the first dose of study drug. For subjects randomized but not dosed, Rx Day calculated relative to randomization.

- a. If time is collected in vital signs, restrict to records prior to the first dose of study drug.
- b. The minimum of upper bound and first dose date of study drug on or after Week 16 (and within 105 days of last dose for safety analyses). If time is collected in vital signs, restrict to records prior to the first dose of study drug on or after Week 16.

Table 5. Visit Windows for Laboratory and ECG Parameters for Part A (Safety_A Population)

Window Label	Target Day	Time Window
Baseline	1	≤ 1
Week 4	29	[2, 71]
Week 16	113	[72, 155 ^a]

Rx Day calculated relative to the first dose date of study drug. For subjects randomized but not dosed, Rx Day calculated relative to randomization.

- a. The minimum of upper bound and first dose date/time on or after Week 16 (and within 105 days of last dose for safety analyses).

Table 6. Visit Windows for Other Efficacy Endpoints Only Collected at Week 16 in Part A (ITT_A Population)

Window Label	Target Day	Time Window
Baseline	1	≤ 1
Week 16	113	[2, 225 ^a]

Rx Day calculated relative to the first dose date of study drug. For subjects randomized but not dosed, Rx Day calculated relative to randomization.

- a. The minimum of upper bound and first dose date of study drug on or after Week 16.

Table 7. Visit Windows for Local Tolerability for Part A (Safety_A Population)

Window Label	Target Day	Time Window
Week 1	8	[2,15]
Week 3	22	[16, 25]
Week 4	29	[26, 71]
Week 16	113	[72, 155 ^a]

Rx Day calculated relative to the first dose of study drug. For subjects randomized but not dosed, Rx Day calculated relative to randomization.

- a. The minimum of upper bound and first dose date of study drug on or after Week 16 (and within 105 days of last dose for safety analyses) (and within 105 days of last dose for safety analyses). If time is collected in vital signs, restrict to records prior to the first dose of study drug on or after Week 16.

Table 8. Visit Windows for Analysis of PASI and sPGA in Part B (ITT_B_RR/ITT_B_R/ITT_B_NR/ITT_B_RZB/PP_B_RR Populations)

Window Label	Target Day	Time Window
Entry of B	1	≤ 1
Week 20	29	[2, 43]
Week 24	57	[44, 71]
Week 28	85	[72, 99]
Week 32	113	[100, 127]
Week 36	141	[128, 155]
Week 40	169	[156, 183]
Week 44	197	[184, 211]

Rx Day calculated relative to the first dose of study drug in Part B. For subjects re-randomized but not dosed in Part B, Rx Day calculated relative to the IRT date of re-randomization evaluation.

Table 9. Visit Windows for Laboratory and ECG Parameters for Part B (Safety_B_RR Population)

Window Label	Target Day	Time Window
Entry of B	1	≤ 1
Week 28	85	[2, 141]
Week 44	197	[142, 211]
Week 48 (EOT + 4 Weeks)	225	[212, 239 ^a]

Rx Day calculated relative to the first dose of study drug in Part B. For subjects re-randomized but not dosed in Part B, Rx Day calculated relative to the IRT date of re-randomization evaluation.

a. The minimum of upper bound and 105 days of last dose for safety analyses.

Table 10. Visit Windows for Vital Signs for Part B (Safety_B_RR Population)

Window Label	Target Day	Time Window
Entry of B	1	≤ 1
Week 20	29	[2, 43]
Week 24	57	[44, 71]
Week 28	85	[72, 99]
Week 32	113	[100, 127]
Week 36	141	[128, 155]
Week 40	169	[156, 183]
Week 44	197	[184, 211]
Week 48 (EOT + 4 Weeks)	225	[212, 239 ^a]

Rx Day calculated relative to the first dose of study drug in Part B. For subjects re-randomized but not dosed in Part B, Rx Day calculated relative to the IRT date of re-randomization.

a. The minimum of upper bound and 105 days of last dose for safety analyses.

Table 11. Visit Windows for Other Efficacy Endpoints Only Collected at Week 44 in Part B (ITT_B_RR/ITT_B_R/ITT_B_NR/ITT_B_RZB/PP_B_RR Populations)

Window Label	Target Day	Time Window
Entry of B	1	≤ 1
Week 44	197	[2, 393]

Rx Day calculated relative to the first dose of study drug in Part B. For subjects re-randomized but not dosed in Part B, Rx Day calculated relative to the IRT date of re-randomization.

Table 12. Visit Windows for Local Tolerability for Part B (Safety_B_RR Population)

Window Label	Target Day	Time Window
Week 28	85	[2, 141]
Week 44	197	[142, 253 ^a]

Rx Day calculated relative to the first dose of study drug in Part B. For subjects re-randomized but not dosed in Part B, Rx Day calculated relative to the IRT date of re-randomization.

a. The minimum of upper bound and 105 days of last dose for safety analyses.

Note. There is no local tolerability at re-randomization and after EOT.

Table 13. Visit Windows for Laboratory and ECG Parameters for ALL_RZB Population

Window Label	Target Day	Time Window
Baseline	1	≤ 1
Week 4	29	[2, 71]
Week 16	113	[72, 155]
Week 28	197	[156, 253]
Week 44	309	[254, 323]
Week 48 (EOT + 4 Weeks)	337	[324, 351 ^a]

Rx Day calculated relative to the first dose of risankizumab.

a. The minimum of upper bound and 105 days of last dose of risankizumab for safety analyses.

Table 14. Visit Windows for Vital Signs for ALL_RZB Population

Window Label	Target Day	Time Window
Baseline	1	$\leq 1^a$
Week 4	29	[2, 43]
Week 8	57	[44, 71]
Week 12	85	[72, 99]
Week 16	113	[100, 127]
Week 20	141	[128, 155]
Week 24	169	[156, 183]
Week 28	197	[184, 211]
Week 32	225	[212, 239]
Week 36	253	[240, 267]
Week 40	281	[268, 295]
Week 44	309	[296, 323]
Week 48 (EOT + 4 Weeks)	337	[324, 351 ^b]

Rx Day calculated relative to the first dose of risankizumab.

- a. If time is collected in vital signs, restrict to records prior to the first dose of risankizumab.
- b. The minimum of upper bound and 105 days of last dose of risankizumab for safety analyses.

Table 15. Visit Windows for Local Tolerability Parameters for ALL_RZB Population

Window Label	Target Day	Time Window
Week 1	8	[2, 15]
Week 3	22	[16, 25]
Week 4	29	[26, 71]
Week 16	113	[72, 155]
Week 28	197	[156, 253]
Week 44	309	[254, 323 ^a]

Rx Day calculated relative to the first dose of risankizumab.

- a. The minimum of upper bound and 105 days of last dose of risankizumab for safety analyses.

The time windows specified below will be used for the summary of study drug injections of each period.

Table 16. Visit Windows for Summary of RZB Injections for Part A

Window Label	Target Day	Time Window
Week 0	1	≤ 1
Week 4	29	[2, 57 ^a]

Rx Day calculated relative to the first dose of study drug.

a. Before the first dose on or after Week 16.

Table 17. Visit Windows for Summary of RZB Self-Administration Questionnaire in Part A

Window Label	Target Day	Time Window
Week 4	29	[2, 57 ^a]

Rx Day calculated relative to the first dose of study drug.

a. Before the first dose on or after Week 16.

Table 18. Visit Windows for Summary of RZB Injections for Part B and RZB Self-Administration Questionnaire

Window Label	Target Day	Time Window
Week 16	1	≤ 1
Week 20	29	[2, 57]
Week 28	85	[58, 99]
Week 32	113	[100, 127]

Rx Day calculated relative to the first dose of study drug in Part B.

Table 19. Visit Windows for Summary of ADA Injections for Part A

Window Label	Target Day	Time Window
Week 0	1	≤ 1
Week 1	8	[2, 15]
Week 3	22	[16, 29]
Week 5	36	[30, 43]
Week 7	50	[44, 57]
Week 9	64	[58, 71]
Week 11	78	[72, 85]
Week 13	92	[86, 99]
Week 15	106	[100, 113]

Rx Day calculated relative to the first dose of study drug.

Table 20. Visit Windows for Summary of ADA Injections for Part B

Window Label	Target Day	Time Window
Week 17	8	[1, 15]
Week 19	22	[16, 29]
Week 21	36	[30, 43]
Week 23	50	[44, 57]
Week 25	64	[58, 71]
Week 27	78	[72, 85]
Week 29	92	[86, 99]
Week 31	106	[100, 113]
Week 33	120	[114, 127]
Week 35	134	[128, 141]
Week 37	148	[142, 155]
Week 39	162	[156, 169]
Week 41	176	[170, 183]

Rx Day calculated relative to the first dose of study drug in Part B.

Definition of Missing Data Imputation

No global imputation is taking place at the database level. Efficacy related imputations are outlined in Section 10.0. There is no imputation for missing values in the safety analyses.

Rounding of Numeric Results

Rounding will be performed for presentation of results. No rounding will be performed before or during analyses. The ROUND function of SAS will be used to round results.

When dichotomizing continuous variables, associated continuous variables will be rounded to 9 decimal points before applying the cutoff point to determine the response status (for example, percent change from baseline in PASI score will be rounded to 9 decimal places before comparing to 90%).

The mean and median will be rounded for presentation to 1 decimal more than the data entered into the database. The standard deviation will be rounded to 2 decimal places more than the data entered into the database. The minimum and maximum values will be presented as entered into the database.

Probabilities will be rounded to 3 decimal places before assignment of statistical significance and will be presented in rounded format. Probabilities that round to zero or are reported by SAS as zero will be presented as "< 0.001." Probabilities that round to 1 or are reported by SAS as 1 will be presented as "> 0.999."

7.0 Demographics, Baseline Characteristics, Medical History, and Previous/Concomitant Medications

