At Visit 5 (Week 4), Visit 8 (Week 16), Visit 9 (Week 20), Visit 11 (Week 28) and Visit 12 (Week 32) the patient self-administers BI 655066 (active or placebo) at the study site under supervision of study personnel. The two injections at these dosing visits should be administered within approximately 5 minutes. The study personnel will complete a study drug self-administration questionnaire for the BI 655066 (active or placebo) self-administrations by patients (refer to [Section 5.6.2](#) and [Appendix 10.8](#)).

BI 655066 (active and matching placebo) as well as adalimumab (active or matching placebo) will be administered as a subcutaneous injection in the abdomen (preferably lower abdomen) or thigh. The two BI 655066 (active or matching placebo) injections done subsequently within approximately 5 minutes should be at least 2 cm apart and should not be close to a vein. The injection sites should avoid sites of psoriasis involvement as well as sites where the skin is tender, bruised, erythematous, or indurated, and should be alternated to other areas for subsequent doses. Further information regarding injection details will be provided in the ISF. The dosing time to be entered in the eCRF is always the time of administration of the first syringe.

For study site visits, investigators and patients are instructed to adhere to the regular allowed time window according to the [Flow Chart](#) (i.e. ± 1 day at Visit 3; ± 3 days at Visits 4 to 14 and at EOT Visit; ± 7 days at EOO Visit). In the rare event that a patient comes too late to a scheduled visit it must be decided whether the delayed visit should still be performed or should be skipped. [Table 4.1.4: 1](#) shows the upper limits for extended time windows up to which study visits can still be performed

Table 4.1.4: 1 Upper Limits for extended time windows for study visits

Visit	Week	Scheduled Visit Day	Upper limit of delay (Days)	Upper limit (Day)
V3	Week 1	Day 8	+ 6	Day 14
V4	Week 3	Day 22	+ 6	Day 28
V5	Week 4	Day 29	+ 27	Day 56
V6	Week 8	Day 57	+ 27	Day 84
V7	Week 12	Day 85	+ 27	Day 112

Table 4.1.4: 1 Upper Limits for extended time windows for study visits (cont'd)

Visit	Week	Scheduled Visit Day	Upper limit of delay (Days)	Upper limit (Day)
V8*	Week 16	Day 113	+ 13	Day 126*
V9	Week 20	Day 141	+ 27	Day 168
V10	Week 24	Day 169	+ 27	Day 196
V11	Week 28	Day 197	+ 27	Day 224
V12	Week 32	Day 225	+ 27	Day 252
V13	Week 36	Day 253	+ 27	Day 280
V14	Week 40	Day 281	+ 27	Day 308

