*if Day 126 is exceeded, Visit 8 (Week 16) will be performed, but patient will continue their previous treatment

There is an exception for Visit 8 (Week 16). This visit will not be skipped. If the upper limit of 126 days for Visit 8 (Week 16) is exceeded, Visit 8 will be performed, but the patient will continue with their previous treatment, irrespective of PASI score.

Adalimumab (active or placebo) home administrations should occur with a time window of ± 3 days. The distance between two adalimumab (active or placebo) administrations should not be less than 11 days. The time window of ± 3 days can be utilized for planning of home administrations. If the minimum distance of 11 days cannot be adhered to, the respective administration should be skipped and the next scheduled dose should be administered.

The injections at each visit, including dummy injections of placebo necessary in order to assure blinding are presented in [Table 4.1.4: 2](#).

Table 4.1.4: 2 Dosing Schedule

Dosing	Patients only on BI 655066**	Patients starting with adalimumab and switching to BI 655066** at Week 16	Patients only on Adalimumab
Randomisation (Visit 2)	Active BI 655066 and Placebo adalimumab*	Placebo 655066 and Active adalimumab*	Placebo 655066 and Active adalimumab*
Week 1 (Visit 3)	Placebo adalimumab	Active adalimumab	Active adalimumab

Table 4.1.4: 2 Dosing Schedule (cont'd)

Dosing	Patients only on BI 655066**	Patients starting with adalimumab and switching to BI 655066** at Week 16	Patients only on Adalimumab
Week 3 (Visit 4)	Placebo adalimumab	Active adalimumab	Active adalimumab
Week 4 (Visit 5)	Active BI 655066	Placebo 655066	Placebo 655066
Week 5	Placebo adalimumab	Active adalimumab	Active adalimumab
Week 7	Placebo adalimumab	Active adalimumab	Active adalimumab
Week 9	Placebo adalimumab	Active adalimumab	Active adalimumab
Week 11	Placebo adalimumab	Active adalimumab	Active adalimumab
Week 13	Placebo adalimumab	Active adalimumab	Active adalimumab
Week 15	Placebo adalimumab	Active adalimumab	Active adalimumab
Week 16 (Visit 8)	Active BI 655066	Active BI 655066	Placebo 655066
Week 17	Placebo adalimumab	Placebo adalimumab	Active adalimumab
Week 19	Placebo adalimumab	Placebo adalimumab	Active adalimumab
Week 20 (Visit 9)	Placebo 655066	Active BI 655066	Placebo 655066
Week 21	Placebo adalimumab	Placebo adalimumab	Active adalimumab
Week 23	Placebo adalimumab	Placebo adalimumab	Active adalimumab
Week 25	Placebo adalimumab	Placebo adalimumab	Active adalimumab

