10.1.4 Missing Data Imputations

Missing data will be imputed using the following methods for the efficacy analyses:

- Non-Responder Imputation (NRI): the NRI analysis will categorize any subject who has a missing value at a specific visit as a non-responder for that visit. The only exception is when the subject is a responder both before and after this specific visit window, within the same analysis period, then the subject will be categorized as a responder for the visit. The NRI will be the primary approach in the analyses of categorical variables.
- Last Observation Carried Forward (LOCF): The LOCF analyses will use the completed evaluation from the previous visit within the particular analysis period for efficacy measures assessed to impute missing data at later visits in the same analysis period. Baseline efficacy evaluations will not be carried forward. Of note, post-baseline observations from Part A can be carried

forward to the ITT_B_RZB subjects since treatment is the same. LOCF will be the primary approach in the analyses of continuous variables, and the secondary approach in the analyses of categorical variables.

- As-Observed Cases (OC): The as-observed analysis will not impute values for missing evaluations, and thus a subject who does not have an evaluation on a scheduled visit will be excluded from the as-observed analysis for that visit. As-observed analysis will be the secondary approach in the analysis of continuous variables.
- Multiple Imputation (MI): The MI analysis will be used as sensitivity approach to impute missing data in primary and ranked secondary endpoints. The variables to be included in the imputation model are listed below. If MI is not applicable due to the nature of our data (e.g., MCMC algorithm does not converge), logistic regression or mixed effect model repeat measurement (MMRM) methods will be applied as sensitivity approach, whichever applicable.

The Multiple Imputation analysis will be carried out in three steps.

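### SAP Table 4 closes the Week 16 PASI/sPGA window at Day 127, so an observed Visit 8 value from Day 128 on can be scored as failure on both co-primaries; the effect is small and the fix is one line

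*SAP*

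**What the plan says.** **Conduct.** Protocol 4.1.4 tells sites to skip or perform delayed visits according to Table 4.1.4: 1, where the Visit 8 limit is Day 126. It then makes Visit 8 an exception: "There is an exception for Visit 8 (Week 16). This visit will not be skipped". Beyond the limit, "If the upper limit of 126 days for Visit 8 (Week 16) is exceeded, Visit 8 will be performed, but the patient will continue" on the previous treatment, whatever the PASI score. Lateness is described as uncommon ("In the rare event that a patient comes too late to a scheduled visit"), and no rate is given.

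**Windows.** SAP 6.0, Table 4 ("Visit Windows for PASI/sPGA and Vital Signs for Part A (ITT_A/PP_A/Safety_A Populations"), sets the Week 16 window for PASI, sPGA and vital signs at Rx Days 100 to 127. Footnote b can only shorten it: "The minimum of upper bound and first dose date of study drug on or after Week 16". Subject to the same kind of cap, Week 16 runs to Day 155 in Table 5 (laboratory, ECG) and Table 7 (local tolerability), and to Day 225 in Table 6 (efficacy endpoints collected only at Week 16 in Part A).

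**Missing values.** Under SAP 10.1.4, "the NRI analysis will categorize any subject who has a missing value at a specific visit as a non-responder for that visit". The exception is a subject who responds both before and after the visit window within the same analysis period. SAP 10.2 makes this the primary approach for the co-primaries, with LOCF and multiple imputation as sensitivity analyses.

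**The concern.** The protocol takes care to obtain Visit 8 however late it is, on unchanged treatment. The SAP then has no place in Part A for a PASI or sPGA recorded on Day 128 or later. Week 16 is the last scheduled Part A visit, so no later Part A window can pick the value up, and an observed co-primary result can be replaced by imputed failure. The per-protocol set PP_A has no visit-timing criterion and inherits the problem. LOCF would carry the previous visit forward and multiple imputation would impute, so neither planned sensitivity analysis clearly uses the observed value. At stake are a slightly diluted treatment difference if lateness is equal across arms, and a shift in either direction if it is not.

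**Working it through.** **1. Where Day 127 comes from.** SAP 6.0 splits the interval between adjacent visits at which a measure is collected.
- PASI/sPGA, Week 16 (Day 113) and Week 20 (Day 141): (113 + 141)/2 = 127.
- Laboratory/ECG, Week 16 and Week 28 (Day 197): (113 + 197)/2 = 155.
- Table 6: 113 + 112 = 225.

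All three bounds reproduce. But Week 20 is a Part B visit, and Table 8 counts Part B days from the first Part B dose. Within Part A no later PASI visit competes for the value, and footnote b already keeps data from after the first Week 16 or later dose out of Part A.

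**2. What counts as Week 16, by date of Visit 8.** This assumes that the first study drug dose on or after Week 16 is the one given at Visit 8.

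| Visit 8 on | PASI, sPGA, vital signs | Laboratory, ECG, local tolerability | DLQI and similar |
|---|---|---|---|
| Days 126, 127 | yes | yes | yes |
| Days 128 to 155 | no | yes | yes |
| Days 156 to 225 | no | no | yes |

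If a Week 17 home injection (nominal Day 113 + 7 = 120) came first, the footnotes would close every one of these windows at that dose, and nothing from the late visit would count. The documents do not say whether a patient holds a Week 17 syringe before Visit 8.

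**3. The plan's own power figures.** Inputs from protocol 7.7 and SAP 4.3: 300 per arm, two-sided 0.05, PASI 90 of 70% v 50% (65% as the lower risankizumab assumption), sPGA 0/1 of 85% v 70%. The formula is the normal approximation with pooled variance under the null:

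n = [1.960·√(2p̄(1−p̄)) + 1.2816·√(p₁(1−p₁) + p₂(1−p₂))]² / (p₁−p₂)²

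At 70% v 50%: [1.960·√0.48 + 1.2816·√0.46]² / 0.04 = 124 per arm, as stated. The other Week 16 entries reproduce within one patient per arm. At 300 per arm, power for each endpoint taken alone is 99.9% (70 v 50), 96.2% (65 v 50) and 99.3% (sPGA), consistent with the stated 90% or more.

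**4. Effect of the window.** Let f be the fraction with Visit 8 after Day 127 (assumed). Suppose late patients respond at their arm's planned rate and every late responder becomes a failure. Each rate is then multiplied by (1−f), and the PASI 90 difference is 20(1−f) points. One patient is 1/300 = 0.33 points of an arm.

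| f, both arms | Late per arm | PASI 90 difference | Power 70 v 50 | Power 65 v 50 | Power sPGA |
|---|---|---|---|---|---|
| 1% | 3 | 19.8 | 99.9% | 95.8% | 99.1% |
| 3% | 9 | 19.4 | 99.8% | 95.0% | 98.6% |
| 5% | 15 | 19.0 | 99.7% | 94.1% | 97.9% |

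**5. Lateness in one arm only.**

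| f, one arm | Risankizumab late: difference 70(1−f) − 50 | Power 65 v 50 | Power sPGA | Adalimumab late: difference 70 − 50(1−f) |
|---|---|---|---|---|
| 1% | 19.3 | 94.6% | 98.6% | 20.5 |
| 3% | 17.9 | 89.9% | 94.9% | 21.5 |
| 5% | 16.5 | 82.8% | 86.5% | 22.5 |

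**The case against.** The differing bounds follow one stated midpoint rule applied to different collection schedules, so they are a convention and not a slip. The protocol nowhere says that a PASI after Day 126 is the Week 16 endpoint; it says only that the visit takes place and no longer drives allocation. A strict window with non-responder imputation is a defensible choice, and Day 127 is within a day of the protocol's own limit. All of this stands. It means that the two documents can be applied together, but it does not explain why an observed pre-dose value on unchanged treatment should be treated as missing when no other Part A visit needs the slot.

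Several stronger readings are tempting, and the documents do not support them:

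- **That the co-primaries alone are shut out.** Vital signs share the Table 4 bound, and laboratory data drop out from Day 156.
- **That the value is thrown away.** Table 8 can still use it as the entry value for Part B.
- **That failure is certain.** A Visit 7 delayed to Days 100 to 112, which Table 4.1.4: 1 permits, would itself supply the Week 16 value. A late pre-dose Visit 8 can also be read as lying after the window but still in Part A, so a Week 12 responder who responds again then could be imputed a responder. Protocol 7.5 has the before-and-after rule without a same-period limit, which widens that possibility.
- **That the primary result is at risk.** The trial is double-blind and double-dummy, late visits are called rare, and nothing suggests lateness in one arm only.

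**Conclusion.** The gap is real on the plain text of Table 4, but conditional and small. It affects only patients whose Visit 8 falls on Day 128 or later, who have no other PASI/sPGA in Days 100 to 127, and who are not rescued by the imputation exception. For them the primary analysis replaces an observed co-primary result with failure.

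With 1% to 3% late in each arm, the 20-point difference falls to no lower than 19.8 to 19.4 points, and power stays above the planned 90%. That floor assumes equal lateness, late patients responding at their arm's planned rate, and every late responder being lost. The late fraction is an assumption, because the documents give none. A material effect needs lateness that differs by arm, in which case the difference could move either way. The change is worth making because it is cheap and uses observed data, not because the trial's conclusion depends on it.

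**What to change.** Before database lock, amend the Week 16 row of SAP Table 4 for PASI and sPGA:

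1. Assign the assessment taken at Visit 8, before the Visit 8 dose, to Week 16 up to Day 155, the bound that Tables 5 and 7 already use. Name the Visit 8 dose as the cap in place of the first dose on or after Week 16, so that an earlier Week 17 home injection cannot close the window.
2. Keep the rule that the assessment closest to Day 113 is used.
3. Report by arm how many Week 16 values fell after Day 127.
4. Keep the Day 127 window with non-responder imputation as a sensitivity analysis, and state whether a late Visit 8 counts as after the window for the imputation exception.

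The cost is one table row, a count and one extra run. The downside is that a few assessments up to 155 − 113 = 42 days (six weeks) late would count as Week 16; the sensitivity analysis shows whether they matter.
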